# **RETURN TO ALLERGAN**

# **Synopsis**

#### NUMBER AND TITLE OF STUDY:

V25L-002: A multicenter, evaluator-blinded, randomized, parallel-group, controlled study of the safety and effectiveness of JUVÉDERM VOLUX™ XC injectable gel for restoring jawline definition

**DEVELOPMENT PHASE:** Pivotal

**STUDY CENTERS:** Up to 20 centers in the United States

**NUMBER OF SUBJECTS:** Up to 280 subjects will be enrolled and up to 216 subjects will be randomized.

**OBJECTIVES:** The objectives of this study are to evaluate the safety and effectiveness of JUVÉDERM VOLUX™ XC (hereafter, VOLUX XC) injectable gel in adults seeking to restore jawline definition.

#### Study design:

This is a multicenter, evaluator-blinded, randomized, parallel-group, controlled study of the safety and effectiveness of VOLUX XC hyaluronic acid (HA) injectable gel to restore a loss of jawline definition. Successfully screened subjects will be randomized to either a treatment or control group (3:1 ratio, respectively).

Subjects randomized to the treatment group will receive treatment on Day 1. After treatment completion (initial and touch-up if touch-up administered), they will be followed for safety and effectiveness for 12 months, with an optional maintenance treatment at Month 12 and additional 3 months of follow-up for safety and effectiveness.

Subjects randomized to the control group will complete a 6-month no-treatment control period. After control period completion, they will have the option to exit the study or receive a delayed-treatment. After treatment completion (initial and touch-up if touch-up administered), subjects will be followed for effectiveness for 6 months and for safety for 12 months without optional maintenance treatment. After follow-up completion (12 months), they will exit the study.

At the Screening visit, after written informed consent (IC) has been given, the Treating Investigator (TI, or a designee) will document the subject's demographics, height, weight, vital signs, Fitzpatrick skin phototype, race, and history of sun exposure, smoking and tobacco use, and medical, surgical, dental, and cosmetic procedures. Female subjects of childbearing potential will undergo urine pregnancy testing. Subjects will undergo 3-dimensional (3D) facial digital images. The Evaluating Investigator (EI) will rate the subject on the 5-grade photonumeric Allergan Loss of Jawline Definition Scale (ALJDS) to determine eligibility for the study. The TI will ensure the subject's anatomy is amenable to at least 1-grade improvement on the ALJDS.

#### Treatment group:

Before treatment on Day 1, for subjects randomized to the treatment group, the following activities will be performed:

- Subject assessments:
  - o FACE-Q Satisfaction with Lower Face and Jawline questionnaire
  - o FACE-Q Appraisal of Lines: Marionette questionnaire
  - o Jaw Functional Limitation Scale
- EI assessment of facial sensation
- Recording of subject pronunciation video
- TI (or designee) assessment of vision (Snellen visual acuity, confrontational visual fields, and ocular motility)

The TI will use supplied 27 G 1/2" needles and/or 25 G 1 1/2" cannulas to inject VOLUX XC to the pre- and post-jowl sulci, chin, marionette lines, and angle of the mandible to restore jawline definition, provide a smooth contour, and achieve an aesthetically pleasing result. Topical or local anesthesia or ice will be applied as necessary. Injectable anesthesia may also be used but must be limited to the treatment area and cannula insertion site.

On the day of treatment, after injection, the following activities will be performed:

- TI assessments
  - product moldability
  - o adverse events (AEs)

- o recording of concomitant medications and procedures
- TI (or designee) assessments
  - Vision (Snellen visual acuity, confrontational visual fields, and ocular motility) approximately 30 minutes after treatment
- Subject assessments
  - o procedural pain on an 11-point scale
  - o daily safety e-diary to record the presence and severity of injection site responses (ISRs) for up to 30 consecutive days after treatment starting on the day of treatment.

Subjects will receive a safety follow-up telephone call at Day 3. If any change to vision is reported during a telephone follow-up or unscheduled phone call, the subject will be asked to come in to the investigational site immediately or will be instructed to receive appropriate care, which may include referral to a retinal specialist. Subjects will return for an office visit at Day 14 to undergo 3D facial digital imaging and complete the Jaw Functional Limitation questionnaire; at that visit, the TI will also perform all safety assessments and the TI (or designee) will perform vision assessments. The subject will not be assessed by the EI at the Day 14 Visit.

At Day 30, if the TI judges that an ALJDS score improvement of at least 1 grade has not been achieved on each side, a touch-up treatment is recommended. If the TI judges that an ALJDS score improvement of at least 1 grade has been achieved on each side, a touch-up may be performed if agreed upon by the subject and the TI. The touch-up treatment visits, procedures, and follow-up are identical to those for the initial treatment. If no touch-up is performed, that visit becomes the Month 1 visit, and the visit is conducted as described below.

Follow-up visits for safety and effectiveness will occur at 1, 3, 6, 9, and 12 months after initial and touch-up, if applicable, are complete. At each visit, the following activities will be performed:

- 3D facial digital imaging
- Recording of pronunciation video
- EI effectiveness assessments
  - ALJDS
  - o improvement in jawline area using the Global Aesthetic Improvement Scale (GAIS)
- EI safety assessments
  - o facial sensation
- TI safety assessments
  - o AEs
  - o recording of concomitant medications and procedures
- Subject assessments
  - o FACE-Q Satisfaction with Lower Face and Jawline questionnaire
  - Subject's Satisfaction with Treatment
  - Natural Look and Natural Feel of the treatment area
  - O Subject's willingness to recommend the treatment (Month 6 and Month 12 visits only after initial treatment, and Month 3 after optional maintenance treatment)
  - o FACE-Q Appraisal of Lines: Marionette
  - o Jaw Functional Limitation Scale questionnaire
  - o improvement in jawline area using the GAIS

After completion of the Month 12 Visit, subjects will be offered an optional maintenance treatment. Subjects who decline maintenance treatment will exit the study. Subjects who agree to receive maintenance treatment will be followed for 3 additional months and then exit the study. The procedures and assessments to be performed at maintenance treatment and at the 4 follow-up visits (Day 3, Day 14, and Months 1 and 3) after maintenance treatment are identical to those after the initial treatment, with the exception that no touch-up will be offered and the product characteristics won't be recorded.

Subjects who are randomized to the treatment group and decide to exit the study at any point before the Month 12 Visit must complete the Early Exit Visit procedures in addition to all applicable visit procedures.

**Control group**: Subjects randomized to the control group will complete a 6-month no-treatment control period following randomization with office visits at Months 1, 3, and 6. At each of these office visits, the following activities will be performed:

• 3D facial digital imaging

- Recording of pronunciation video
- EI effectiveness assessments
  - ALJDS
  - o improvement in the jawline definition using the GAIS
- EI safety assessment of facial sensation
- TI safety assessments
  - o AEs
  - o recording of concomitant medications and procedures

Subjects in the control period who decide to exit the study at any point before the Month 6 Visit must complete the Early Exit Visit procedures in addition to all applicable visit procedures.

After the Month 6 procedures are complete, subjects will be offered to enter the delayed-treatment period. During this part of the study they will receive treatment (initial with optional touch-up) after which they will be followed for safety and effectiveness for 6 months:

- 3D facial digital imaging
- Recording of pronunciation video
- TI safety assessments
  - o AEs
  - o recording of concomitant medications and procedures
- TI (or designee) safety assessments
  - O Vision (Snellen visual acuity, confrontational visual fields, and ocular motility [before and approximately 30 minutes after treatment, and Day 14 after treatment])
- EI effectiveness assessment
  - o ALJDS
  - o improvement in jawline area using the GAIS
- EI safety assessment of facial sensation
- Subject assessments
  - o procedural pain on an 11-point scale
  - daily safety e-diary to record the presence and severity of ISRs for up to 30 consecutive days after treatment starting on the day of treatment.
  - Jaw Functional Limitation Scale questionnaire
  - o FACE-Q Satisfaction with Lower Face and Jawline questionnaire
  - o improvement in jawline area using the GAIS

Control subjects who receive optional treatment will also complete safety phone calls at 9 and 12 months.

Control subjects in the delayed-treatment period who decide to exit the study at any point before the Month 6 Visit must complete the Early Exit Visit procedures in addition to all applicable visit procedures.

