FACE-Q Satisfaction with Lower	Xf							
Face and Jawline (subject)	Λ							
FACE-Q Appraisal Lines:	$X^{f}$							
Marionette	Λ							
Jaw Functional Limitation Scale	$X^{f}$		X	$\mathbf{X}^{\mathrm{f}}$		X		
(subject)			Λ			Λ		
Facial sensation assessment (EI)	X f			$X^{f}$				
Snellen visual acuity (TI or designee)	X g		X	X g		X		
Confrontational visual fields (TI or	X g		X	X g		X		
designee)								
Ocular motility (TI or designee)	X g		X	X g		X		
Pretreatment anesthesia	X			X				
Treatment (TI)	X			X				
Injection ease and product	X			X				
moldability (TI)				Λ				
Procedural pain (subject)	X			X				
ALJDS (EI) h				X				
Safety telephone call		X			X			
Weight							X	
Subject safety e-diary i		Continuou	IS		Continuous			
Concomitant Medications,				Cantinuara			X	
Procedures, Therapies		Continuous						
Adverse Events			(	Continuous			X	

3D = 3-dimensional; ALJDS = Allergan Loss of Jawline Definition Scale; EI = Evaluating Investigator; GAIS = Global Aesthetic Improvement Scale; ITx = initial treatment; IWRS = interactive web response system; Rand = Randomization; TI = Treating Investigator; TTx = touch-up treatment

- a Randomization must occur within 30 days of screening.
- A touch-up treatment is recommended on Day 30 if the TI determines that the subject has not achieved at least a 1-grade improvement on ALJDS on each side. If the TI judges that an ALJDS score improvement of at least 1 grade has been achieved on each side, a touch-up may be performed if agreed upon by the subject and the TI. If a touch-up treatment is not performed, then complete Month 1 visit procedures (Table 3) instead of the Day 30 visit procedures.
- Subjects who discontinue early are to complete applicable study visit procedures and Early Exit Visit procedures.
- d Inclusion criteria 2 and 3 are not repeated.
- e For female subjects of childbearing potential; must be confirmed negative prior to injection.
- f Done before study treatment.
- On initial and touch-up treatment days, vision assessments performed before treatment and approximately 30 minutes after treatment.

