Subjects who discontinue early, ie, before the Month 6 Visit, are to complete applicable study visit procedures and Early Exit Visit procedures.

For female subjects of childbearing potential, must be confirmed negative before randomization.

Table 5 Schedule of Visits and Procedures: Control Group (Delayed-Treatment Period)

1 able 5	Schedule (	)1 V 15115 a	anu 110	ccuui es.	Contro	n Grou	p (Delay	cu-11ca	tillent i	CII	ju)	
Study Period	Day 1 Opt ITx a	Day 3 After Opt ITx	Day 14 After Opt ITx	Day 30/ Opt TTx b	Day 3 After Opt TTx	Day 14 After Opt TTx	Month 1	Month 3	Month 6	Month 9	Month 12/ Study Exit	Early Exit Visit c
Visit Window	Month 6 Visit +14 Days	-1/+2 Days	±3 Days	-2/+10 Days	-1/+2 Days	±3 Days	-2/+10 Days	±10 Days	±10 Days		±10 Days	
Urine pregnancy test d	X			X					X			X
Snellen visual acuity (TI or designee)	X e		X	X e		X						
Confrontational visual fields (TI or designee)	X e		X	X e		X						
Ocular motility (TI or designee)	X e		X	X e		X						
Pretreatment anesthesia	X			X								
Treatment injections (TI)	X			X								
Procedural pain (subject)	X			X								
Jaw Functional Limitation Scale (subject)	$X^{f}$		X	$X^{f}$		X	X	X	X			
FACE-Q Satisfaction with Lower Face and Jawline (subject)	$X^{\mathrm{f}}$						X	X	X			
3D facial digital imaging	X			$X^f$			X	X	X			
Pronunciation video recording	$X^{f}$			$X^{f}$			X	X	X			
GAIS (subject)							X	X	X			
ALJDS (EI) g							X	X	X			
Facial sensation assessment (EI)	$X^{f}$			$X^f$			X	X	X			
GAIS (EI)							X	X	X			
Weight									X			
Safety telephone call		X			X						X	
Subject safety e-diary h	Continuous Continuous											
Concomitant medications, procedures, therapies	Continuous Monitoring						X					
Adverse Events	Continuous Monitoring								X			

Approval Date: 11-Mar-2019

- EI = Evaluating Investigator; GAIS = Global Aesthetic Improvement Scale; ITx = initial treatment; Opt = optional; TI = Treating Investigator; TTx = touch-up treatment
- a Optional initial treatment can occur same day or within 14 days after the Month 6 Visit. If optional initial treatment occurs on the same day as the Month 6 Visit, duplicate assessments do not have to be repeated.

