# 4.3.3 Methods for Blinding

The Evaluating Investigator (EI) and the image analysis technician will be blinded to treatment. The EI will not be present during the injection procedures. As the image files will be accessed by the blinded image analysis technician, the image files will not reveal subject treatment randomization or the timepoint at which the image was captured.

Prior to site activation, the sponsor will ensure that study site staff, including the investigator, are trained on the importance of maintaining EI blind.

The Treating Investigator (TI) and study coordinators will not be blinded to treatment, but will secure the randomization and other records (eg, records of study treatments and prior study assessments) from potential discovery by the blinded EI. The TI will not discuss the randomized treatment assignments with or in the presence of the EI. Subjects will not be blinded to treatment and will be instructed not to speak with the EI about treatment. The Principal Investigator (PI) maintains the study role of TI in this study.

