#### 6.6 Withdrawal Criteria

The subject may withdraw at will at any time.

If a subject has a positive urine pregnancy test at the time of the initial or maintenance treatment visit, the subject will not be eligible for treatment and will be withdrawn from the study. If a subject has a positive urine pregnancy test after treatment, she will continue all scheduled visits and non-treatment procedures. The pregnancy will be followed as described in Section 10.3.

In addition, a subject must be withdrawn from the study if he/she:

- receives any dermal filler or fat injection to the chin area
- undergoes facelift or facial reconstructive surgery
- receives treatment with hyaluronidase in the chin area
- changes his/her decision about having photographs taken

A subject may also be withdrawn at the discretion of physician.

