5.4.2. Main Analytical Approach

For the secondary effectiveness endpoints of GAIS responder status at Month 6 as assessed by the EI and as assessed by the participant, the 95% CI will be provided for the proportion of responders within each treatment group, where applicable. These analyses will be performed on the mITT population.

No multiplicity adjustments will be made for the 2 GAIS responder rates since these endpoints are descriptive in nature.

For the secondary effectiveness endpoint of change from baseline in FACE-Q Satisfaction with Lower Face and Jawline overall score at Month 6 for the treatment group in the mITT population, a 2-sided paired t-test at the 5% level will be used to determine if the mean overall satisfaction score at Month 6 is statistically greater than that at baseline. This test will be

[figure not shown]
performed only if the co-primary endpoints are met. For items with missing data (which includes more than 1 response was selected, not applicable was selected, or a question was skipped), insert the mean of the completed items into the total sum score. If less than 50% of the questions have been answered (ie, number of missing items is 2 or more), then the overall score will be missing. The summary score including the imputation of missing items is rounded to the nearest integer and converted to the Rasch transformed score using the conversion table in Section 6.5.1.

Secondary effectiveness analyses are summarized in Table 5-5.

Table 5-5 Secondary Effectiveness Analyses

Endpoint	Description	Missing Data Handling Rule	Methodology
GAIS responder status as assessed by the EI at Month 6	Number (%) of responders by treatment group	Observed data is used; no imputation is needed	Categorical descriptive statistics
GAIS responder status as assessed by the participant at Month 6	Number (%) of responders by treatment group	Observed data is used; no imputation is needed	Categorical descriptive statistics
Mean change from baseline in Rasch transformed score of FACE-Q satisfaction with lower face and jawline at Month 6	Mean change from baseline within the treatment group	No imputation. Only observed data will be used in the analysis.	2-sided paired t-test

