taken on or after the start date of study treatment for treatment group or on or after the randomization date for control group.

Actual and change from baseline values for overall (including all items) and the 3 subscales of mastication, mobility, and verbal and non-verbal communication from the Jaw Functional Limitation Scale will be summarized using descriptive statistics by treatment group for the VT and VMT populations. The overall score will be computed as the mean of the available items. Details on the algorithm can be found in Section 6.5.3. Baseline for the control group during TP is defined as the last non-missing value prior to receiving optional treatment.

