12. The imputation for the missing items of FACE-Q Satisfaction with Lower Face and Jawline and FACE-Q Appraisal Lines: Marionette were added to Section 5.4.2 and 5.5, respectively.
13. Added the definition of baseline for the control group for FACE-Q Satisfaction with Lower Face and Jawline in Section 5.5 since this assessment is not done on the control group during the control period.
14. Added clarification on the subset of participants on whom the analyses of FACE-Q Appraisal Lines: Marionette will be performed in Section 5.5. Additionally, the definition of responder on FACE-Q Appraisal Lines: Marionette was added to this section.
15. The wording of “responder status” was added to the “number (%) of responder” analysis for the endpoints of ALJDS, GAIS (EI and participant), FACE-Q Satisfaction with Lower Face and Jawline, and FACE-Q Appraisal Lines: Marionette in Table 5-6 for clarity.
16. The analysis of ISR in Section 5.6.4 was revised to include: (1) ISR summary by maximum duration instead of simply by duration and (2) analysis of “other symptoms” based on the coded terms assigned by the Medical Safety Physician.
17. Added clarification regarding analysis for 2-point discrimination and pronunciation video as well as definition of baseline in the control group during TP for Jaw Functional Limitation Scale in Section 5.6.6.
18. Subgroup analysis of the primary effectiveness endpoint by baseline ALJDS was added in Section 5.7.1.
19. A data listing to tabulate the COVID-19 related data collected during the study is added to Section 5.7.2.
20. Since no interim analysis regarding the primary and secondary endpoints was performed the text regarding the same was deleted in Section 5.8.
21. A summary for baseline ALJDS at jaw level as well as subject level was added in Section 6.3.2.
22. Changed the population for medical history listing from mITT population to all randomized participants in Section 6.3.4.

CONFIDENTIAL

JUVÉDERM VOLUX™ XC

Statistical Analysis Plan V25L-002

23. Removed the summary of prior and concomitant medications and changed the population for prior and concomitant medications listing from mITT population to all randomized participants in Section 6.3.5.
24. Added details regarding analysis windows for safety assessments in Section 6.4.1.2.

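### VOLUX subjects give their baseline FACE-Q and jaw-function answers after they know their allocation, and one of these baselines feeds the single-arm FACE-Q test

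*Protocol*

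**What the plan says.** **Day 1 questionnaires.** The synopsis assigns FACE-Q Satisfaction with Lower Face and Jawline, FACE-Q Marionette and the Jaw Functional Limitation Scale (JFLS) with the words "Before treatment on Day 1, for subjects randomized to the treatment group, the following activities will be performed". Protocol Table 2 lists all three below the IWRS randomization row, with a note that requires only that they precede injection. Table 4, the control group's no-treatment schedule, contains none of them. SAP 6.2.2 says of FACE-Q Satisfaction that a separate control baseline had to be defined "since this assessment is not done on the control group during the control period". For JFLS, SAP 5.6.6 states: "Baseline for the control group during TP is defined as the last non-missing value prior to receiving optional treatment".

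**Blinding.** Protocol 4.3.3: "Subjects will not be blinded to treatment".

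**Use of the baseline.** For FACE-Q Satisfaction at Month 6 in the treatment group, SAP 5.4.2 says "a 2-sided paired t-test at the 5% level will be used to determine" whether the mean exceeds baseline, provided the primary endpoint is met; protocol 8.3.2 agrees. The two GAIS rates are called descriptive in both places. SAP 5.4.1 does mention Fisher's exact test for GAIS, but SAP 5.4.2 and Table 5-5 give descriptive statistics only. FACE-Q is thus the one secondary endpoint with a success test consistently set out.

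**Pregnancy test.** Table 2 footnote e: "For female subjects of childbearing potential; must be confirmed negative prior to injection". Table 4 footnote c: "For female subjects of childbearing potential, must be confirmed negative before randomization". Under protocol 6.6, after a positive test at the initial treatment visit, "the subject will not be eligible for treatment and will be withdrawn from the study".

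**The concern.** A form meant only for VOLUX subjects cannot be handed out until the arm is known, so as written these baselines follow the allocation. A subject who has just learned that treatment is minutes away may rate the present jawline differently from one who does not yet know. A lower rating inflates the later change; a higher one hides part of it. In a two-arm comparison with the same timing in both arms, such a shift would largely cancel. In a paired test within one arm it goes straight into the result.

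The protocol takes this precaution for the primary endpoint, whose ALJDS baseline is the evaluator's rating before randomization (8.2.1). The subject-reported baseline, which is more open to expectation, does not get it. The SAP's general baseline rule (5.1) works on dates. Randomization and first injection fall on the same day, so that rule does not separate values given before allocation from values given after it.

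The blinded evaluator's Day 1 facial sensation test is also listed below the randomization row in both tables. The evaluator may therefore meet subjects who already know their arm and have been asked not to mention it.

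**Working it through.** **Step 1. Order of events.** Section 6.2.2 has one visit for both arms. After randomization, VOLUX subjects go on to injection that day and controls finish what remains of the visit, so procedures after allocation are expected. The FACE-Q forms and JFLS are in Table 2 and not in Table 4. With the synopsis wording, the natural reading is allocation, then forms, then injection.

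**Step 2. What one answer is worth.** The SAP 6.5.1 conversion table runs 0, 9, 16, 22, 28, 34, 40, 46, 52, 59, 66, 72, 78, 84, 92, 100. The steps are 9, 7, 6, 6, 6, 6, 6, 6, 7, 7, 6, 6, 6, 8, 8. Moving one of the five items by one category changes the score by 6 to 9 points.

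**Step 3. Number of pairs.** The planned VOLUX arm is 144 to 162, with 15% drop-out to Month 6: 144 × 0.85 = 122 and 162 × 0.85 = 138.

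**Step 4. Smallest significant mean shift with no true change.** Shift = t(0.975, n−1) × SD / √n. The documents give no SD of change; 15, 20 and 25 are assumed.

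| n | SD 15 | SD 20 | SD 25 |
|---|---|---|---|
| 122 | 2.69 | 3.58 | 4.48 |
| 138 | 2.52 | 3.37 | 4.21 |

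**Step 5. As a share of subjects moving one item one step, all in the same direction.** The extremes are 2.52/9 = 28% and 4.48/6 = 75%. At SD 20 with a 6-point step, the share is 3.37/6 = 56% to 3.58/6 = 60%.

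**Step 6. Smaller shifts.** Chance of a significant apparent improvement with no true change (noncentral t, n = 120; nominal 2.5% in that direction):

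| Baseline lowered by | In points if SD = 20 | Chance |
|---|---|---|
| 0.05 SD | 1 | 7.8% |
| 0.1 SD | 2 | 19.1% |
| 0.2 SD | 4 | 58.4% |

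These are scenarios. The documents do not say that any such shift occurs.

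**Step 7. Sample-size figures.** The exact power of the 1-sided Fisher test for 120 versus 40 at 80% versus 40% is 99.41%, which agrees with the stated figure of more than 99%. No sample-size figure is wrong because of this point.

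**Step 8. Pregnancy-test footnotes.** One sets the deadline at injection and the other at randomization, for a visit at which the arm is not yet known; 6.2.2 refers to Table 2 only. Because injection follows randomization on the same day (6.2.3.1), a single negative test before randomization meets both. Under the Table 2 wording alone, a site could test after the randomization call, and a positive result would then lead to withdrawal in the VOLUX arm only. As a check on size, assume 0.5%, 1%, 2% or 5% of 144 VOLUX subjects were lost this way: 1, 2, 3 or 8 subjects. Taking all of them from the 120 evaluable leaves the Fisher power at 99.4% each time.

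**The case against.** The strongest reply is that the repair removes little. The test is an uncontrolled before-after comparison, and subjects answer at Month 6 knowing they were treated. Moving the form ahead of the randomization call only replaces certainty of treatment with a 3:1 chance of it, and controls are offered treatment later anyway. The FACE-Q items ask about the past week, which should dampen the effect of news a few minutes old. The test is run only if the primary endpoint is met. Nothing in the documents supports a shift of any particular size. All of this stands, and it limits the weight of the point. It does not remove it: knowledge of allocation at baseline is avoidable, whereas the lack of blinding at Month 6 is not.

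Three stronger readings are tempting, and the documents do not support them.

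- *That baselines in general depend on the arm.* The ALJDS baseline precedes randomization in both arms. Pronunciation video and facial sensation are scheduled at randomization in both. No between-arm FACE-Q test is planned, and JFLS is only described.
- *That the two pregnancy-test footnotes cannot both be followed, so withdrawals must differ by arm.* One test before randomization satisfies both. Table 2 lists the test above the randomization row, and the Day 1 eligibility recheck omits only inclusion criteria 2 and 3, so the pregnancy exclusion is checked again. Arm-specific withdrawal is permitted by the Table 2 wording, not required by it.
- *That such a withdrawal would break the randomized comparison.* The subject remains in the protocol's ITT population, and in the SAP's mITT population given an ALJDS baseline on both sides.

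**Conclusion.** The point holds for the subject-reported baselines. VOLUX subjects complete both FACE-Q forms and the JFLS after allocation and without blinding, and the FACE-Q Satisfaction value is the starting point of a single-arm test with nothing to offset a shift. The possible size is an assumption throughout: 2.5 to 4.5 points for an SD of change of 15 to 25 and 122 to 138 pairs, or roughly 28% to 75% of subjects moving one item one step in the same direction. The direction is unknown, so the shift could flatter the product or hide benefit. The primary endpoint, the planned between-arm comparisons and the sample size are unaffected. The change is worth making because it costs so little, not because bias has been shown. The pregnancy-test footnotes are a separate, minor inconsistency with negligible effect on the primary analysis.

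**What to change.** In protocol 6.2.2 and Tables 2 and 4, require every subject to complete the two FACE-Q forms, the JFLS, the pronunciation video and the evaluator's sensation test before the IWRS randomization call. For Day 1, change the Table 2 note that ties these assessments to treatment so that it ties them to randomization, and align the synopsis. The evaluator's Day 1 contact then also takes place before there is any allocation to disclose.

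Cost: at most 54 controls answer 5 + 7 + 20 = 32 items once, with small changes to the eCRF, the visit schedule and the SAP. The SAP should say that these control values have no planned control-period follow-up. It should also say whether the delayed-treatment JFLS baseline, now the last available value before optional treatment, may reach back to Day 1 when the later form is missing. For subjects already randomized the order cannot be changed; the report should state the timing beside the paired test.

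Separately, reconcile Table 2 footnote e, Table 4 footnote c and protocol 6.6 so that one stated timing applies to the shared visit.
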